4.7.3. Clinical Laboratory Evaluation

Laboratory measurements will be analyzed using continuous data (change from baseline) and categorical or ordinal data (proportion of treatment-emergent abnormalities). If there are multiple records of laboratory measurements at baseline or postbaseline visit, the last record will be used. Summaries and analyses of continuous data (change from baseline) will be performed using both conventional and International System of Units (SI units).

Change from baseline to post-baseline visit at which laboratory measurements are taken will be compared between treatment groups using an MMRM model on the safety analysis set. The model will include the fixed, categorical effects of treatment, visit, and treatment-by-visit interaction as well as the continuous effects of ranked baseline value and age at baseline. This analysis will be done separately for each laboratory analyte.

Treatment differences in the proportion of participants with treatment-emergent high or treatment-emergent low or treatment-emergent abnormal laboratory values at (1) anytime and (2) each scheduled post-baseline visit will be assessed using Fisher's exact test. Treatment-emergent high or low laboratory abnormality will be based on SI unit. For each laboratory

analyte, only participants who were low or normal at baseline and have at least 1 post-baseline will be included in the denominator when computing the proportion of participants with treatment-emergent high. Similarly, only participants who were high or normal at baseline and have at least 1 post baseline will be included in the denominator when computing the proportion of participants with treatment-emergent low. In addition, treatment differences in the proportion of participants who have normal baselines with a change to abnormal high or abnormal low values at any post-baseline visits will be summarized.

The proportion of participants with treatment-emergent clinically significant changes from a low value or normal value at all baselines at any time in ALT and total bilirubin will be summarized by treatment group. Clinically significant changes of interest at any time are: ALT ≥ 3 x upper limit of normal (ULN) and total bilirubin ≥ 2 x ULN, AST ≥ 3 x ULN, ALT ≥ 5 x ULN, ALT ≥ 10 x ULN, and total bilirubin ≥ 2 x ULN. Additionally, Hy's Law analysis will be conducted by comparing treatment groups with regard to the proportion of participants with (ALT ≥ 3 x ULN OR AST ≥ 3 x ULN) AND total bilirubin ≥ 2 x ULN at any time. Comparisons between treatment groups will be carried out using Fisher's Exact test. When criteria are met for hepatic evaluation and completion of the hepatic safety case report form (CRF), investigators are required to answer a list of questions pertaining to the participant's history, relevant pre-existing medical conditions, and other possible causes of liver injury. A listing of the information collected on the hepatic-safety CRF will be generated.

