23. ALT $\geq 2.5X$ ULN of the performing laboratory, AST $\geq 2.5X$ ULN, TBL $\geq 1.5X$ ULN, or ALP $\geq 2X$ ULN at screening.

Note: Participants with TBL $\geq 1.5X$ ULN are not excluded if they meet all of the following criteria for Gilbert's syndrome:

- Bilirubin is predominately indirect (unconjugated) at screening (direct bilirubin within normal limits).
- Absence of liver disease.
- ALT, AST, and ALP $\leq 1X$ ULN at screening.
- Hemoglobin is not significantly decreased at screening.

Prior/Concomitant Therapy

24. Have known allergies to donanemab or aducanumab, related compounds, or any components of the formulation.
25. Have had prior or current treatment with donanemab or aducanumab.

Prior/Concurrent Clinical Study Experience

26. Prior or current participation in any active or passive immunotherapy study targeting A β , unless documentation of receipt of placebo.
27. Are currently enrolled in any other interventional clinical trial involving a study intervention or any other type of medical research judged not to be scientifically or medically compatible with this study.
28. Have participated, within the last 30 days, in any clinical trial involving a study intervention. Participation in observational studies may be permitted upon review of the observational study protocol and approval by the sponsor.

Other Exclusions

29. Are study personnel directly involved with the execution of this study, and/or their immediate families. Immediate family is defined as a spouse, parent, child, or sibling, whether biological or legally adopted.
30. Are Lilly employees or are employees of TPOs directly involved in the study which requires exclusion of their employees, or have study partners who are Lilly employees or are employees of TPOs involved in a study which requires exclusion of their employees.

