8.2.3. Clinical Safety Laboratory Tests

- See Appendix 2 for the list of clinical laboratory tests to be performed and the SoA for the timing and frequency.
- The investigator must review the laboratory results, document this review, and report any clinically relevant changes occurring during the study as an AE. The laboratory results must be retained with source documents unless a Source Document Agreement or comparable document cites an electronic location that accommodates the expected retention duration. Clinically significant abnormal laboratory findings are those which are not associated with the underlying disease, unless judged by the investigator to be more severe than expected for the participant's condition.
- All laboratory tests with values considered clinically significantly abnormal during participation in the study or within the follow-up period after the last dose of study intervention after the last dose of study intervention should be repeated until the values return to normal or baseline or are no longer considered clinically significant by the investigator or medical monitor.
 - If such values do not return to normal/baseline within a period of time judged reasonable by the investigator, the etiology should be identified and the sponsor notified.
 - All protocol-required laboratory assessments, as defined in Appendix 2, must be conducted in accordance with the SoA, standard collection requirements, and laboratory manual.
- If laboratory values from non-protocol specified laboratory assessments performed at an investigator-designated local laboratory require a change in participant management or are considered clinically significant by the investigator (e.g., SAE or AE or dose modification), then report the information as an AE.

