8.2.6. Hepatic Safety Monitoring

Close hepatic monitoring

Laboratory tests (Appendix 6, Section 10.6), including ALT, AST, ALP, TBL, D. Bil, GGT, and CK, should be repeated within 48 to 72 hours to confirm the abnormality and to determine if it is increasing or decreasing, if one or more of these conditions occur:

If a participant with baseline results of ...	develops the following elevations:
ALT or AST <1.5x ULN	ALT or AST \geq 3x ULN
ALP <1.5x ULN	ALP \geq 2x ULN
TBL <1.5x ULN	TBL \geq 2x ULN (except for participants with Gilbert's syndrome)
ALT or AST \geq 1.5x ULN	ALT or AST \geq 2x baseline

ALP $\geq 1.5x$ ULN	ALP $\geq 2x$ baseline
TBL $\geq 1.5x$ ULN	TBL $\geq 1.5x$ baseline (except for participants with Gilbert's syndrome)

If the abnormality persists or worsens, clinical and laboratory monitoring, and evaluation for possible causes of abnormal liver tests should be initiated by the investigator in consultation with the Lilly-designated medical monitor. At a minimum, this evaluation should include physical examination and a thorough medical history, including symptoms, recent illnesses (for example, heart failure, systemic infection, hypotension, or seizures), recent travel, history of concomitant medications (including over-the-counter), herbal and dietary supplements, history of alcohol drinking and other substance abuse.

Initially, monitoring of symptoms and hepatic biochemical tests should be done at a frequency of 1 to 3 times weekly, based on the participant's clinical condition and hepatic biochemical tests. Subsequently, the frequency of monitoring may be lowered to once every 1 to 2 weeks, if the participant's clinical condition and lab results stabilize. Monitoring of ALT, AST, ALP, and TBL should continue until levels normalize or return to approximate baseline levels.

Comprehensive hepatic evaluation

A comprehensive evaluation should be performed to search for possible causes of liver injury if one or more of these conditions occur:

If a participant with baseline results of...	develops the following elevations:
ALT or AST $< 1.5x$ ULN	ALT or AST $\geq 3x$ ULN with hepatic signs/symptoms ^a , or ALT or AST $\geq 5x$ ULN
ALP $< 1.5x$ ULN	ALP $\geq 3x$ ULN
TBL $< 1.5x$ ULN	TBL $\geq 2x$ ULN (except for participants with Gilbert's syndrome)
ALT or AST $\geq 1.5x$ ULN	ALT or AST $\geq 2x$ baseline with hepatic signs/symptoms ^a , or ALT or AST $\geq 3x$ baseline
ALP $\geq 1.5x$ ULN	ALP $\geq 2x$ baseline

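### SAP 4.7.3 applies a last-record-per-visit rule to categorical laboratory tables too, so a retest filed under the same visit can replace the abnormal value that prompted it

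*SAP*

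**What the plan says.** SAP 4.7.3 opens by setting the scope of the laboratory analyses: "Laboratory measurements will be analyzed using continuous data (change from baseline) and categorical or ordinal data (proportion of treatment-emergent abnormalities"). The next sentence gives the only record-selection rule in the section: "If there are multiple records of laboratory measurements at baseline or postbaseline visit, the last record will be used". It names no exception.

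The same section then plans these categorical outputs:

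- Treatment-emergent high, low or abnormal values, both at any time and at each scheduled post-baseline visit.
- ALT at or above 3, 5 and 10 times ULN, AST at or above 3 times ULN, and bilirubin at or above 2 times ULN, all at any time, in participants with low or normal values at their baselines (written in the plural).
- A Hy's Law comparison that joins an ALT or AST elevation with bilirubin: "AND total bilirubin ≥ 2 x ULN at any time".

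The protocol says when extra records arise. Under Protocol 8.2.3, clinically significantly abnormal values "should be repeated until the values return to normal or baseline or are no longer considered clinically significant by the investigator or medical monitor". Under Protocol 8.2.6, liver tests that cross stated limits "should be repeated within 48 to 72 hours to confirm the abnormality and to determine if it is increasing or decreasing", and monitoring goes on until they normalise or return to about baseline.

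**The concern.** A last-record rule is a harmless tie-breaker when duplicate records are interchangeable. Here they often are not: one documented reason for a second record is that the first was abnormal. If the second record carries the same visit label and has fallen below the cut-off, the table shows no event, although the participant had one and was retested because of it.

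Liver safety in the two arms is at stake. Post-baseline chemistry is scheduled only at Weeks 24, 52 and 76, plus early termination, so few other samples would show the same elevation. The SAP also has no rule assigning a retest to the originating visit or to an unscheduled one. Two programmers could therefore produce different counts from the same data.

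**Working it through.** The plan gives no figure on this point, so there is nothing to reproduce. The check sets the texts side by side and then illustrates the scale.

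**1. Does the rule reach the categorical tables?** It follows immediately on the sentence naming both kinds of analysis, and no later sentence gives another rule. As written, it does.

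**2. Do the retest triggers meet the tabulated cut-offs?** For participants with baseline below 1.5 times ULN, Protocol 8.2.6 asks for a retest at ALT or AST of 3 times ULN or more and at bilirubin of 2 times ULN or more (Gilbert's syndrome excepted for bilirubin). SAP 4.7.3 tabulates the same limits. In these participants, a tabulated case is one for which the protocol calls for a second record.

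**3. Can the retest share the visit?** The visit window at Weeks 24, 52 and 76 is ±7 days, and 48 to 72 hours is 2 to 3 days. A sample drawn on the target day would have its retest on day +2 or +3, inside the window. A sample drawn on day +6 would have it on day +8 or +9, outside. Sharing is possible but not certain.

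**4. Which way does the error run?** Within one visit the last value can never exceed the maximum. For a high cut-off, the last-record count is therefore equal to or below the worst-record count. If the retest is higher than the first value, nothing is lost.

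**5. One hypothetical participant.** At a visit ALT is 6 times ULN and bilirubin 2.5 times ULN. Three days later, under the same visit label, they are 2.5 and 1.5 times ULN.

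| Table | Last record | Worst record |
|---|---|---|
| ALT ≥3x ULN | no (2.5) | yes (6) |
| ALT ≥5x ULN | no (2.5) | yes (6) |
| Bilirubin ≥2x ULN | no (1.5) | yes (2.5) |
| Hy's Law | no | yes |

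**6. Does the hepatic CRF listing catch the loss?** Its triggers in Protocol 8.2.6, for participants with low baselines, are:

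- ALT at or above 5 times ULN on two or more consecutive tests;
- bilirubin at or above 2 times ULN;
- ALP at or above 2 times ULN on two or more consecutive tests;
- a serious hepatic event;
- discontinuation for a hepatic event.

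The participant in step 5 would be listed through bilirubin. With normal bilirubin, the same ALT course (6, then 2.5) meets no ALT trigger. Nor does an isolated ALT of 3 to 5 times ULN that resolves.

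**7. Scale, on assumed rates.** The documents give no laboratory event rates. Let p be the true incidence, q the share of cases whose last same-visit record is below the cut-off, and n = 100 per arm (about 200 randomized 1:1). Cases shown = n × p × (1 − q).

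| p (assumed) | q = 0 | 25% | 50% | 75% | 100% |
|---|---|---|---|---|---|
| 2% | 2 | 1.5 | 1 | 0.5 | 0 |
| 5% | 5 | 3.75 | 2.5 | 1.25 | 0 |
| 10% | 10 | 7.5 | 5 | 2.5 | 0 |

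One chosen contrast: 8 versus 1 cases per 100 gives Fisher p = 0.035. If half of the 8 are lost and the 1 is kept, 4 versus 1 gives p = 0.37. This shows only that small counts are sensitive. It does not predict what this trial will show.

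**The case against.** The strongest reply is that the rule only chooses between records within a visit. SAP 4.7.3 separates any-time tables from by-visit tables, and its liver thresholds and Hy's Law comparison are any-time. Its plural baselines also do not fit a single last-record baseline. On that reading the liver tables already use every record. This is plausible, and it makes the loss in those tables conditional. The SAP does not state it, however, and the by-visit categorical tables stay exposed whenever a retest shares the visit label.

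Other replies stand in part:

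- A reader might infer that the last record is by design the recovered one. The documents do not support that. The early retest is meant to show whether the value is rising or falling, so it may confirm or exceed the first. Follow-up at 1 to 3 times weekly, then every 1 to 2 weeks, can run past the visit window. Same-visit duplicates can also arise from paired local and central samples (Protocol Appendix 2).
- The general repeat rule says should, and covers only clinically significant abnormalities. The liver triggers, by contrast, are numeric.
- Safeguards exist. A single bilirubin at or above 2 times ULN (baseline below 1.5 times ULN, no known Gilbert's syndrome) triggers the hepatic CRF, which the SAP will list. Clinically relevant laboratory changes are reported as adverse events. These narrow the gap but leave isolated enzyme rises to the investigator's judgment.

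**Conclusion.** The point holds in conditional form. As written, the last-record rule covers categorical laboratory tables, and a same-visit retest can remove the abnormal value from them. The by-visit tables are directly exposed. The any-time, threshold and Hy's Law tables are exposed unless any-time means all records.

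The loss cannot be sized from the documents. For the any-time tables it is zero if retests are stored as unscheduled visits and all records are used. Otherwise it depends on how many retests share the visit label and fall below the cut-off. The counts in the working rest on assumed rates. Efficacy analyses are not affected.

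Two further inferences are not supported. A reader might infer that the Hy's Law comparison needs a time window between the enzyme and bilirubin elevations. Pairing at any time can only over-flag, which is a defensible choice for a screen, and the documents give no basis for a particular window. A reader might also infer that participants with Gilbert's syndrome will distort the liver tables. The normal-baseline condition in SAP 4.7.3 already keeps those with raised screening bilirubin out of the threshold summary, so the point is partly handled, although the Hy's Law sentence does not repeat the condition.

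**What to change.** In SAP 4.7.3:

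1. Limit the last-record rule to baseline selection and change-from-baseline summaries, where it is acceptable.
2. For by-visit categorical tables, use the worst post-baseline value within the visit.
3. For any-time, ALT/AST/bilirubin threshold and Hy's Law tables, use the worst value across all scheduled, repeat and unscheduled post-baseline records.
4. State how retests are assigned to visits.
5. Reconcile the last-record baseline (also the general definition in SAP 4.1) with the plural baselines in the liver paragraph.

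No new data are needed. The cost is SAP wording and a little programming. Abnormality counts may rise slightly, and some counted values will be ones that a retest did not confirm. Showing index and retest values together in a listing would let the reader judge those.

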TBL $\geq 1.5x$ ULN	TBL $\geq 2x$ baseline (except for participants with Gilbert's syndrome)

^a Hepatic signs/symptoms are severe fatigue, nausea, vomiting, right upper quadrant abdominal pain, fever, rash, and/or eosinophilia $> 5\%$.

At a minimum, this evaluation should include physical examination and a thorough medical history, as outlined above, as well as tests for PT-INR; tests for viral hepatitis A, B, C, or E; tests for autoimmune hepatitis; and an abdominal imaging study (for example, ultrasound or CT scan).

Based on the participant's history and initial results, further testing should be considered in consultation with the Lilly-designated medical monitor, including tests for hepatitis D virus, cytomegalovirus, Epstein-Barr virus, acetaminophen levels, acetaminophen protein adducts, urine toxicology screen, Wilson's disease, blood alcohol levels, urinary ethyl glucuronide, and blood phosphatidylethanol. Based on the circumstances and the investigator's assessment of the participant's clinical condition, the investigator should consider referring the participant for a hepatologist or gastroenterologist consultation, magnetic resonance cholangiopancreatography, endoscopic retrograde cholangiopancreatography, cardiac echocardiogram, or a liver biopsy.

Additional hepatic data collection (hepatic safety CRF) in study participants who have abnormal liver tests during the study

Additional hepatic safety data collection in hepatic safety CRF should be performed in study participants who meet 1 or more of the following 5 conditions:

1. Elevation of serum ALT to $\geq 5x$ ULN on 2 or more consecutive blood tests (if baseline ALT $< 1.5x$ ULN)
 - In participants with baseline ALT $\geq 1.5x$ ULN, the threshold is ALT $\geq 3x$ baseline on 2 or more consecutive tests
2. Elevated TBL to $\geq 2x$ ULN (if baseline TBL $< 1.5x$ ULN) (except for cases of known Gilbert's syndrome)
 - In participants with baseline TBL $\geq 1.5x$ ULN, the threshold should be TBL $\geq 2x$ baseline
3. Elevation of serum ALP to $\geq 2x$ ULN on 2 or more consecutive blood tests (if baseline ALP $< 1.5x$ ULN)
 - In participants with baseline ALP $\geq 1.5x$ ULN, the threshold is ALP $\geq 2x$ baseline on 2 or more consecutive blood tests
4. Hepatic event considered to be a SAE
5. Discontinuation of study drug due to a hepatic event

Note: the interval between the two consecutive blood tests should be at least 2 days.

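### SAP 4.7.3 counts single-analyte liver threshold elevations only from low or normal baselines, so an isolated ALT, bilirubin or (by inference) AST elevation in a participant admitted with a raised value is left out of the arm comparison

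*SAP*

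**What the plan says.** SAP 4.7.3 plans several categorical liver outputs, and their denominators differ.

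- **Threshold summary.** It covers "treatment-emergent clinically significant changes from a low value or normal value at all baselines at any time in ALT and total bilirubin". The list that follows begins "Clinically significant changes of interest at any time are: ALT ≥ 3 x upper limit of normal (ULN) and total bilirubin ≥ 2 x ULN" and goes on to AST at 3×, ALT at 5× and 10×, and bilirubin at 2× ULN.
- **Treatment-emergent high, each analyte.** Here "only participants who were low or normal at baseline and have at least 1 post-baseline will be included in the denominator".
- **Normal-to-abnormal summary.** This is the "proportion of participants who have normal baselines with a change to abnormal high or abnormal low values at any post-baseline visits".
- **Treatment-emergent low, each analyte.** Here "only participants who were high or normal at baseline and have at least 1 post baseline will be included in the denominator".
- **Hy's Law.** The text reads "Additionally, Hy's Law analysis will be conducted by comparing treatment groups with regard to the proportion of participants with" ALT or AST at 3× ULN together with bilirubin at 2× ULN. No baseline condition is stated.

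Change from baseline is also modelled by MMRM on the safety set, and hepatic CRF data are listed.

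On entry, Protocol 5.2 criterion 23 excludes "ALT $\geq 2.5X$ ULN of the performing laboratory", AST at the same multiple, and bilirubin at or above 1.5× ULN. An exception for Gilbert's syndrome carries no upper bilirubin limit. Protocol 8.2.6 sets separate rules for raised baselines. For the hepatic CRF, for example: "In participants with baseline ALT $\geq 1.5x$ ULN, the threshold is ALT $\geq 3x$ baseline on 2 or more consecutive tests".

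**The concern.** A normal-baseline filter is natural in a shift-to-high table, because someone already high cannot shift to high. It does less for a count of large multiples of ULN. The ALT 5× and 10× and AST 3× thresholds lie above the entry limits, so no eligible participant meets them at screening, and the same holds for bilirubin 2× outside Gilbert's syndrome. For those rows the filter mainly removes on-study events in people whose baseline was mildly raised.

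Clinical laboratory tests are part of the stated safety objective. With about 200 participants such elevations may be few, so leaving out even one could change how a Fisher comparison reads.

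**Working it through.** The documents state no figure on this point, so there is nothing to reproduce. The check sets the texts side by side and then follows one example.

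**1. Who can enter (Protocol 5.2, criterion 23).** ALT or AST from above 1× to below 2.5× ULN; bilirubin from above 1× to below 1.5× ULN; bilirubin at any higher level under the Gilbert's exception.

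**2. Where a participant with a raised baseline is counted (SAP 4.7.3).**

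| Output | Raised baseline included? |
|---|---|
| Threshold summary, ALT and bilirubin | No, stated |
| Threshold summary, AST | No, by inference: the restricting sentence names only ALT and bilirubin |
| Treatment-emergent high | No, stated |
| Normal-to-abnormal | No, stated |
| Treatment-emergent low | Yes, but says nothing about liver injury |
| Hy's Law | Yes, but needs raised bilirubin as well |
| MMRM of change | Yes, as a contribution to a mean |
| Hepatic CRF listing | Only if a CRF condition is met |

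**3. Size of rise that goes uncounted.** Fold rise = threshold ÷ baseline.

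- ALT baseline 1.5× ULN: 3/1.5 = 2.0, 5/1.5 = 3.3, 10/1.5 = 6.7.
- ALT baseline 2.49× ULN: 3/2.49 = 1.2, 5/2.49 = 2.0, 10/2.49 = 4.0.
- Bilirubin baseline 1.49× ULN: 2/1.49 = 1.3.

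Some of these are real rises. Others, notably from just under an entry limit, could be fluctuation.

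**4. An example.** Baseline ALT 1.8× ULN, later 5.3× ULN, bilirubin normal throughout.

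- The threshold, treatment-emergent-high and normal-to-abnormal tables exclude the participant on baseline.
- Hy's Law is not met, because bilirubin is normal.
- The ALT condition for the hepatic CRF is not met: 5.3/1.8 = 2.9, below 3× baseline, and two consecutive tests would be needed in any case.
- The MMRM includes the value, but a mean does not display one outlier.

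Unless another hepatic CRF condition applies (a bilirubin or ALP criterion, a serious hepatic event, a hepatic discontinuation) or the investigator reports an adverse event, this elevation is in no liver count or hepatic listing.

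**5. Different cut-points.** Protocol 8.2.6 divides participants at 1.5× ULN and applies absolute multiples of ULN to everyone below that. The SAP divides them at the upper limit of normal. A participant with baseline ALT between 1× and 1.5× ULN is therefore judged by absolute thresholds in monitoring but is absent from the SAP's absolute-threshold table. For baselines at or above 1.5× ULN, the Protocol has baseline-relative thresholds that no SAP table uses.

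**6. How many.** Number outside the restricted tables for an analyte = 200 × s, where s is the share with a raised baseline. The documents do not give s. For assumed values of 2%, 5%, 10% and 15% the number is 4, 10, 20 and 30. These are participants, not events; the documents give no event rate.

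**The case against.** The strongest reply is that defining treatment emergence from a normal baseline is a coherent choice, and that other routes cover those left out. Much of this stands.

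- A reader might infer that participants with raised baselines appear in no categorical ALT or bilirubin table. The documents do not support that. The Hy's Law comparison has no stated baseline condition, and the treatment-emergent-low denominator expressly includes high baselines.
- A reader might also take the AST restriction as stated. It is only implied by AST's place in the list.
- One might try to estimate the share of ALT 3× cases lost. The list does not clearly plan a stand-alone ALT 3× row: its opening item joins ALT 3× with bilirubin 2×, and bilirubin 2× recurs at the end, which suggests a combined criterion. Prevalence and relative risk would both have to be assumed, so no such share is given here.
- Protocol 8.2.3 requires clinically relevant laboratory changes to be reported as adverse events, and SAP 4.7.2 tabulates treatment-emergent events without a laboratory-baseline filter. This route depends on the investigator's judgement, so it supplements a systematic laboratory count but does not replace it.
- An unfiltered bilirubin row would miscount. Under the Gilbert's exception a participant may enter already at or above 2× ULN, and the monitoring and evaluation tables of Protocol 8.2.6 exempt Gilbert's syndrome from their bilirubin triggers. This is right, and the remedy has to deal with it.
- The filter applies alike to both randomized arms, so no bias towards either is shown. That is also correct. The loss is of completeness.

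**Conclusion.** The point holds in a limited form. The single-analyte threshold summary covers ALT 5× and 10×, bilirubin 2×, ALT 3× if it is read as stand-alone, and AST 3× by inference. That summary and the treatment-emergent-high table both omit participants with raised baselines whom the entry criteria admit. An isolated threshold elevation in such a participant is not counted in the arm comparison, and the remaining outputs do not reliably recover it. The number affected is unknown; the 4 to 30 participants above rest wholly on the assumed 2% to 15%. Nothing in the documents shows that these participants are at higher hepatic risk, and criterion 13 excludes serious or unstable hepatic disease. This is a worthwhile improvement to safety reporting. It has no bearing on the co-primary analyses.

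**What to change.** In SAP 4.7.3:

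1. Count ALT, AST and bilirubin threshold elevations in all safety-set participants with a post-baseline value, split by baseline status. Keep the low-or-normal-baseline count as its own row.
2. For bilirubin, show participants with Gilbert's syndrome, or with a baseline already at or above the threshold, on a separate row, and do not count them as treatment-emergent.
3. For baselines of at least 1.5× ULN, add a count using the baseline-relative thresholds already in Protocol 8.2.6, naming which of its sets is used. In practice this concerns ALT and AST, because criterion 23 admits bilirubin at that level only with Gilbert's syndrome.
4. State whether AST falls under the baseline restriction, and whether the first listed item is ALT 3× alone or combined with bilirubin 2×.

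The cost is SAP wording and a few table rows, from data already collected. The downside is that some participants will cross a threshold by fluctuation from a high baseline. The split by baseline status makes those cases visible.
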